APPENDIX I – EORTC QLQ - LC13 Quality of Life Questionnaire (Lung Cancer)

APPENDIX II – Common Terminology Criteria for Adverse Events (CTCAE) version 4.0

1.0 Study Schema

This trial is a seamless phase I/II prospective, single arm, cohort study.

Phase I of the trial will consist of two patients and will serve to conduct quality assurance assessments and to familiarize thoracic surgeons, radiation oncologists, and medical physicists at CancerCare Manitoba and Health Sciences Center in the use and work flow of the Health Canada approved endobronchial implanted real-time tumor tracking transponder beacons (The Calypso™ beacon). Patients in phase I will undergo standard stereotactic ablative radiotherapy (SABR) of a lung tumor with prior endobronchial transponder beacon placement. For phase I, the transponder beacons will be used for comparative localization analyses and SABR treatment setup procedures will be carried out independent of transponder beacon data, however, transponder data will be collected in order to conduct, post-treatment, *in vivo* quality assurance assessments of beacon performance characteristics. Otherwise, the SABR treatment for phase I will consist of the currently accepted standard internal target volume based and standard image guided SABR.

Phase II of this trial will consist of 26 patients who will undergo a specialized form of SABR radiotherapy specifically designed to take full advantage of the real-time tumor tracking ability of the Calypso™ transponder beacons. Specifically, SABR in phase II will consist of smaller radiotherapy treatment volumes employing respiratory gating and smaller planning target volume expansion margins given the superior tumor location telemetry afforded by the Calypso™ beacons. Comparative dosimetric analyses contrasting the traditional ITV/PTV style treatments to those with reduced ITV/PTV margins achieved via Calypso guided SABR will be performed. Patient self-reported quality of life and toxicity assessments will be collected with the goal of facilitating power and sample size calculations for the design of a larger phase III randomized controlled trial of Calypso guided SABR treatment in the future.

Phase I (n=2)

Adults ≥ 18 years of age
T1N0M0 or T2N0M0 (<4cm) NSCLC; or
A single Metastatic Lung Tumor < 4cm
ECOG performance status 0 to 2
Surgically inoperable
Non-Oxygen dependent at baseline

“Standard” Stereotactic Ablative Radiotherapy:

- 1) Endobronchial Calypso Beacon Placement

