3.0 Trial Design

This is a prospective, single arm, seamless phase I/II cohort study (investigator initiated trial) with a planned total accrual of 28 patients.

4.0 Study Population:

Potentially eligible patients are adults with surgically inoperable, biopsy proven or suspected single T1N0 or T2N0 Non-small cell lung cancer tumor or patients with a single pulmonary metastasis (<4 cm maximal tumor dimension) from a known primary malignancy of any histology (either metastatic failure to a single pulmonary site after primary radical treatment, or metastatic progression to a single lung metastasis following palliative chemotherapy with no other sites of uncontrolled disease). Tumors should be located either in the lower lobe, lingula, or right middle lobe of the lung however, patients with upper lobe tumors are eligible as long as the tumors have a respiratory amplitude of ≥ 1 cm. Tumors should be located at least 2 cm from the proximal bronchial tree (non-central tumors).

5.0 Eligibility Criteria:

- 1) Adult ≥ 18 years of age who is surgically inoperable, or refusing surgical management.
- 2) Tumor criteria (a patient must satisfy one of “a”, “b” below to be eligible):
 - a. AJCC 7th edition clinical T1aN0M0, T1bN0M0, or T2aN0M0 (<4cm) Non-small cell lung cancer (adenocarcinoma, squamous cell carcinoma, or NSCLC Not Otherwise Specified) of the middle or lower lobes of the lung*;
 - b. A single pulmonary metastasis (<4cm) of a known primary malignancy of any histology involving the middle or lower lobes of the lung* (either metastatic failure to a single pulmonary site after primary radical treatment, metastatic progression to a single lung

[figure not shown]
metastasis following palliative chemotherapy, or a single pulmonary metastatic lesion of newly diagnosed stage IV malignancy).

*upper lobe tumors are eligible for trial participation if the tumor has a demonstrated tumor motion of ≥ 1 cm in any axis (as assessed by fluoroscopy at the time of bronchoscopy).

- 3) Confirmation of malignancy (a patient must satisfy one of “a”, “b” below to be eligible):
 - a. Tumors accessible by bronchoscopy, image-guided percutaneous biopsy, or other invasive staging methods require biopsy confirmation of malignancy.
 - b. If a tumor is not amenable to a diagnostic biopsy, evidence of growth of the target tumor on serial imaging scans is necessary prior to enrollment. An increase in SUV of the target tumor on serial PET scans is also acceptable.

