- 5) To quantify the potential benefit of continuous monitoring of tumor location using Calypso by comparing it to traditional imaging-based setup.

Phase II:

- 1) To quantitatively assess the differences in irradiated treatment volumes and radiotherapy dose volume metrics for the PTV and healthy thoracic organs at risk between Calypso™ guided respiratory gated SABR and the traditional ITV based radiotherapy.
- 2) To serially quantify the acute and late toxicity of patients undergoing Calypso™ guided SABR using the Common Terminology Criteria for Adverse Events (CTCAE) Version 4.0
- 3) To serially quantify the self-reported quality of life of patients undergoing Calypso Guided SABR using the EORTC QLQ - LC13 questionnaire
- 4) To serially biobank blood and urine samples for patients undergoing radical SABR of lung tumors to allow for the future development of novel prognostic and predictive biomarkers for patients undergoing SABR.
- 5) To serially quantify changes to pulmonary function following SABR treatment

- 6) To demonstrate the benefit of Calypso treatments in reducing patient-specific component of PTV margins

Study Hypotheses:

Phase I: Calypso beacon placement will be safe and well tolerated and will function within their specified tolerances with minimal (sub-millimeter) inter-beacon migration.

Phase II: The Median Planning Target Volume (PTV) of Calypso guided respiratory gated SABR will be 40% smaller than the median PTV volume of standard ITV based SABR treatment with standard PTV margins. Furthermore, thoracic organs at risk will receive significantly less radiotherapy dose when compared to the standard SABR treatment.

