7.0 Study Endpoints:**Primary Endpoints**

Phase I: Mean difference in inter-beacon distance (in millimeters) (at time of 4DCT simulation compared to fractions 1,2, and 3 of SABR)

Phase 2: Mean within patient difference in PTV volumes of standard ITV-based SABR compared to gated SABR utilizing Calypso based PTV margins (expressed as a percentage difference).

Secondary Endpoints:

- 1) Patient self-reported quality of life (EORTC QLQ - LC13 questionnaire)
- 2) Acute and late toxicity - Common Terminology for Criteria for Adverse Events (CTCAE version 4.0)
- 3) Median within patient difference in radiotherapy doses to thoracic Organs at risk
- 4) Median change in FEV1, DLCO, and 6 minute walking distance on room air at baseline compared to follow-up time points.
- 5) Local tumor control (using the RECIST version 1.1 Criteria²⁶)
- 6) Progression Free Survival
- 7) Cancer Specific Survival
- 8) Overall Survival

8.0 Pre-treatment Investigations:

All staging investigations shall be completed within 12 weeks prior to study enrollment.

- 1) History and Physical Exam
- 2) CT scan or MRI of brain
- 3) PET scan
- 4) CT chest and abdomen
- 5) Pulmonary function testing (including spirometry, diffusion capacity, and 6 minute walk test)
- 6) CBC, electrolytes, BUN, Creatinine
- 7) Quantitative beta-HCG (Only if the participant is a premenopausal female).

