Radiotherapy treatment planning: SABR treatment plans will be calculated using the Varian Acuros dosimetric algorithm with inhomogeneity correction. Two co-planar, two-hundred and forty degree arcs of volumetric modulated arc therapy (VMAT) will be the default beam arrangement.

SABR Delivery: SABR will be delivered using the Varian Edge linear accelerator at the KIAM using 10MV flattening filter free photon beams using a dose rate of 2400 MU/min.

Gating Window: The end-exhalation phase (CT50) plus one phase directly preceding (CT40) and following (CT60) will be used as the gating window. CT30 and CT70 may also be included in the gating window.

Chemotherapy: Chemotherapy, immunotherapy, or mutation targeted therapies should be held at least 24 hours prior to the first fraction, and can be restarted 24 hours after the delivery of the last fraction.

Cone Beam CT-based (CBCT) Image Guidance: In phase I of the trial, cone beam CT scans will be performed daily in order to allow for initial image guidance of treatment setup using bony landmarks (vertebral bodies) and soft tissue (tumour). Calypso beacon data will be collected during phase I including inter-transponder geometry.

Calypso Guidance: In Phase II of the trial, calypso beacon data will be used to fine tune initial patient positioning and treatment delivery. The location data from the Calypso beacons will be captured by the Calypso array in order to assess inter-transponder beacon distance, as well as beacon geometric center location relative to the linear accelerator's isocenter. This position is used as the reference for Calypso to provide continuous monitoring. Calypso data will then be used for respiratory gating of the SABR treatment. CBCT imaging may also be performed to verify the soft tissue-beacon correspondence. CBCT images will be evaluated and may be used for patient repositioning if necessary.

Respiratory gating (phase I): For phase I of the trial, the respiratory gating signal will not be used to control the radiation beam delivery, however, Calypso transponder beacons will be used to provide location telemetry for quality assurance and data analysis purposes only.

Respiratory Gating (Phase II): The SABR radiation beam delivery will be gated using the Calypso transponder location data for phase II of the study.

OAR Tolerances (as derived from the RTOG 0618 protocol by Timmerman et. al.):

| Organ | Volume | Dose Constraint (Gy) |

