| | none | minor | none | minor | none | minor | none | minor | |
| 2.0 | <1.2 | 1.2-1.4 | <3.9 | 3.9-4.1 | <28.1 | 28.1-30.1 | <10 | 0-15 | 1.8 |
| 2.5 | <1.2 | 1.2-1.4 | <3.9 | 3.9-4.1 | <28.1 | 28.1-30.1 | <10 | 10-15 | 3.8 |
| 3.0 | <1.2 | 1.2-1.4 | <3.9 | 3.9-4.1 | <28.1 | 28.1-30.1 | <10 | 10-15 | 7.4 |
| 3.5 | <1.2 | 1.2-1.4 | <3.9 | 3.9-4.1 | <28.1 | 28.1-30.1 | <10 | 10-15 | 13.2 |
| 4.0 | <1.2 | 1.2-1.4 | <3.8 | 3.8-4.0 | <30.4 | 30.4-32.4 | <10 | 10-15 | 21.9 |
| 4.5 | <1.2 | 1.2-1.4 | <3.7 | 3.7-3.9 | <32.7 | 32.7-34.7 | <10 | 10-15 | 33.8 |
| 5.0 | <1.2 | 1.2-1.4 | <3.6 | 3.6-3.8 | <35.1 | 35.1-37.1 | <10 | 10-15 | 49.6 |
| 5.5 | <1.2 | 1.2-1.4 | <3.5 | 3.5-3.7 | <37.4 | 37.4-41.7 | <10 | 10-15 | 69.9 |
| 6.0 | <1.2 | 1.2-1.4 | <3.3 | 3.3-3.5 | <39.7 | 39.7-41.7 | <10 | 10-15 | 95.1 |
| 6.5 | <1.2 | 1.2-1.4 | <3.1 | 3.1-3.3 | <42.0 | 42.0-44.0 | <10 | 10-15 | 125.8 |
| 7.0 | <1.2 | 1.2-1.4 | <2.9 | 2.9-3.1 | <44.3 | 44.3-46.3 | <10 | 10-15 | 162.6 |

11.0 Potential Adverse Reactions:

The adverse effects associated with the use of the Calypso transponder beacons are similar in profile to other bronchoscopic procedures such as bronchoscopic biopsies or the implantation of inert gold seed fiducial markers.

Pneumothorax: The most commonly encountered adverse effect of fiducial marker placement is pneumothorax which has a risk of between 2 to 5 percent^{27,28} with the majority of these treated either conservatively or with a pigtail catheter for a day or two²⁴ after the procedure.

COPD Exacerbations: Exacerbations of emphysema or chronic obstructive pulmonary disorder (COPD) have been reported with a risk of up to 11 percent²⁹ in one small case series of 9 patients who had non-calypso beacons implanted. However, several much larger case series reported no COPD exacerbations^{24,27,28} whatsoever.

Beacon Migration: Beacon migration has been reported at a rate of 1%²⁴ using anchored calypso beacons which can lead to the expectoration of the migrated beacon.

Infection: There is a 1% risk of pulmonary infection in the tissue in close proximity to an anchored Calypso beacon²⁴.

Minor Bleeding: There is a small risk of minor local bleeding in the airway implanted with the transponder beacon with a risk similar to other bronchoscopic based procedures, however no pulmonary hemorrhages were reported in the case series using the anchored Calypso lung beacon²⁴.

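### The sub-millimetre beacon-stability hypothesis is assessed by a mean from two patients with no interval, while the same measurement in the Phase II patients has no planned analysis

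*Combined protocol and SAP*

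**What the plan says.** Section 6.0 (Study Hypotheses, Phase I) expects that the beacons "will function within their specified tolerances with minimal (sub-millimeter) inter-beacon migration". The matching objective, to quantify any migration through the inter-beacon distance, appears under Phase I only.

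Section 7.0 gives the Phase I primary endpoint as "Mean difference in inter-beacon distance (in millimeters) (at time of 4DCT simulation compared to fractions 1,2, and 3 of SABR". The Phase II primary endpoint is the PTV comparison, and none of the eight secondary endpoints is inter-beacon distance.

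On numbers, Section 1.0 states "Phase I of the trial will consist of two patients" and "Phase II of this trial will consist of 26 patients"; Section 3.0 gives a "planned total accrual of 28 patients".

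On data collection, the Section 12.0 schedule marks inter-beacon distance at the 4DCT simulation and at each SABR fraction, with no restriction by phase. Section 10.0 (Calypso Guidance) says that in Phase II the beacon location data are "captured by the Calypso array in order to assess inter-transponder beacon distance".

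Section 13.0 describes analyses for PTV, quality of life, toxicity, organ-at-risk metrics, pulmonary function, local control and survival. It has no entry for inter-beacon distance: no estimate, interval, unit of analysis or criterion.

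**The concern.** The hypothesis is quantitative: it sets a 1 mm scale. The endpoint attached to it is a mean over two patients, reported with no stated uncertainty. A mean from two patients says very little about a population mean, so whatever value is observed, the hypothesis can hardly be supported or refuted. The mean is also not stated to be of absolute changes. If signed changes are averaged, a lengthening in one patient or beacon pair can cancel a shortening in another.

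The same measurement, at the same time points, is to be taken in the Phase II patients, and the plan does not say how it will be summarised. Phase II delivery is gated on beacon position with reduced margins, so stable inter-beacon geometry is a premise of the method under study. The plan collects data that could estimate stability usefully and prespecifies only the two-patient part.

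**Working it through.** **The plan's own figure.** The only power statement, in Section 13.0, concerns PTV. With δ = 0.40 × 62.9 = 25.16 cm³, SD = 43.6 cm³, n = 28 and one-sided α = 0.05:

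power = Φ(25.16 / (43.6/√28) − 1.645) = Φ(3.054 − 1.645) = Φ(1.409) = 0.92.

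This reproduces the stated 0.92. It has no bearing on migration, for which the documents give no sample-size reasoning.

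**Inputs for the migration endpoint.** From the documents: n = 2 (Phase I), n = 26 (Phase II), n = 28 (total), and a 1 mm threshold from the hypothesis. Not in the documents: the between-patient SD of the change, the measurement error, and the rate of changes of 1 mm or more. Results are therefore expressed in units of SD or shown over an assumed range.

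**Step 1: precision of the mean.** The 95% half-width is t(0.975, n−1) × SD/√n.

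- n = 2: 12.706/√2 = 8.98, so 8.98 × SD.
- n = 28: 2.052/√28 = 0.388, so 0.39 × SD.
- n = 26: 0.404, so 0.40 × SD.

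**Step 2: SD at which 1 mm can be excluded.** The observed mean plus the half-width must be below 1 mm.

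| Observed mean | SD must be below, n = 2 | SD must be below, n = 28 |
|---|---|---|
| 0 mm | 1/8.98 = 0.11 mm | 1/0.388 = 2.58 mm |
| 0.5 mm | 0.5/8.98 = 0.056 mm | 0.5/0.388 = 1.29 mm |

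**Step 3: half-width over an assumed range of SD.**

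| Assumed SD | Half-width, n = 2 | Half-width, n = 28 |
|---|---|---|
| 0.25 mm | 2.25 mm | 0.10 mm |
| 0.5 mm | 4.49 mm | 0.19 mm |
| 1 mm | 8.98 mm | 0.39 mm |
| 2 mm | 17.97 mm | 0.78 mm |

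At every assumed SD, the two-patient half-width alone exceeds 1 mm and the 28-patient half-width does not.

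**Step 4: illustration on the patient scale.** Suppose no patient shows a change of 1 mm or more. The exact one-sided 95% upper bound on the proportion of such patients is 1 − 0.05^(1/n).

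- 0 of 2: 1 − 0.05^(1/2) = 77.6%.
- 0 of 28: 1 − 0.05^(1/28) = 10.1%.
- The two-sided exact 95% upper limits, 1 − 0.025^(1/n), are 84.2% and 12.3%.
- Counting six beacons (typically three per patient, Section 2.0) as independent, which is generous because they cluster within patients, still gives 1 − 0.05^(1/6) = 39%.

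If 10% of patients truly had such a change (an assumption), two patients would show none with probability 0.9² = 81%, against 0.9^28 = 5.2% for 28. At an assumed 30%, the figures are 0.7² = 49% and less than 0.1%.

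**The case against.** The strongest reply is that Phase I is a run-in. Section 1.0 gives its purpose as quality assurance and team familiarisation, and two patients may suit that. This stands: nothing here says that Phase I is too small for its stated purpose. But the plan also gives those two patients a primary endpoint and a millimetre-scale hypothesis, and that is the part they cannot carry.

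Several stronger readings are tempting, and the documents do not support them:

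- A reader might infer that stability will be declared if no problem is seen in two patients. There is no such rule. The plan states a hypothesis and a continuous mean, with no decision criterion, so the zero-event figures above are only an illustration.
- A reader might infer that a two-patient stability finding would feed the phase III design. Section 1.0 ties phase III power and sample size to quality of life and toxicity, not to migration.
- A reader might take the 1% migration rate in Section 11.0 as a per-beacon rate and compute from it. That section gives no unit, and the rate concerns migration that can lead to expectoration. It neither supports nor contradicts a sub-millimetre claim.
- A reader might say that the Phase II beacon data go unused. Section 10.0 uses them for positioning and gating, allows CBCT verification of the beacon-to-tissue relation, and has a margin review triggered by first-fraction setup errors. These are checks on individual patients. What is missing is a planned cohort estimate.

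**Conclusion.** The point holds in this limited form: the plan attaches a sub-millimetre hypothesis to a two-patient mean without an interval, and prespecifies no analysis of the same measurement in the other 26 patients. Using all 28 cuts the 95% half-width from 8.98 to 0.39 times the SD, a factor of about 23 (8.98/0.388). On the illustrative patient scale, the one-sided bound after zero events falls from 78% to 10%.

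The multipliers need no assumed SD, but they rest on a t-interval with the patient as the unit and on all 28 being evaluable; with 26 the multiplier is 0.40. The SD range and the 10% and 30% rates are assumptions. The PTV endpoint and its power are unaffected.

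**What to change.** Keep the two-patient Phase I result as a descriptive quality-assurance check. Add to Sections 7.0 and 13.0 an analysis of all implanted, evaluable patients (up to 28), and point the Section 6.0 hypothesis to it:

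1. **Main estimate.** For each patient, take the absolute change in each inter-beacon distance from 4DCT to fractions 1 to 3 and average it to one value per patient. Report the mean across patients with a 95% CI. Absolute values stop opposite shifts from cancelling, and one value per patient respects clustering.
2. **Supporting estimate.** Report the proportion of patients with any change of 1 mm or more, with an exact 95% CI. Keep this descriptive: a count of any change over several beacon pairs and three fractions rises with measurement noise, and the documents give no measurement error.
3. **Criterion.** State that the sub-millimetre hypothesis is supported only if the upper confidence limit for the mean absolute change is below 1 mm.

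No new measurements are needed. The cost is small wording changes to the endpoint and analysis sections, with the cross-reference in Section 6.0, and a stability statement that waits for Phase II data. Limits remain. Even 0 of 28 cannot exclude a rate of about 10% (12% on the two-sided interval). Movement between implantation and 4DCT, which a Phase I objective mentions, is outside both the endpoint and the schedule, so this analysis would not capture it.

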|--|---------------------------|
| Age | Mean & Standard Deviation |
| Gender | Percentage |
| Comorbidity (Charlson Index) | Mean & Standard Deviation |
| Smoking History Category (Current smoker, previous smoker, never smoker) | Percentage |
| Smoking Pack-Year History | Mean & Standard Deviation |
| FEV1 (Liters) | Mean & Standard Deviation |
| Diffusion Capacity (%) | Mean & Standard Deviation |
| 6 Minute Walk Test (% of expected distance) | Mean & Standard Deviation |
| Tumor Factors | |
| T-stage (T1, T2) | Percentage |
| Tumor size (cm ³) | Mean & Standard Deviation |
| Tumor location (by lobe) | Percentage |
| Tumor Histology | Percentage |
| Treatment Factors | |
| GTV (cm ³) | Mean & Standard Deviation |
| PTV (cm ³) | Mean & Standard Deviation |
| Maximal observer tumor motion (cm) | Mean & Standard Deviation |
| Radiotherapy Dose Prescription (cGy) | Percentage |
| Radiotherapy Delivery Time Per Fraction | Mean & Standard Deviation |

Study Power:

Power calculations were conducted using the STATA 12.0 statistical software package (College station, Texas). Zhao *et al.*²² carried out dosimetric analyses of lung tumors undergoing SABR lung treatments with similar characteristics (T1-T2N0 NSCLC) to those which would be eligible for this study and found a median PTV volume of 62.9 cm³ (sd 43.6 cm³). Presuming similar sized tumor volumes as Zhao *et al.*, A sample size of 28 patients would yield a power of 0.92 to detect a 40% reduction in the mean PTV volume between standard ITV based SABR treatment as compared to gated calypso guided SABR, with an alpha value of 0.05 and using a 1-sided test for statistical significance.

Endpoints:

Percentage Change in PTV: For each participating patient, the PTV volumes will be calculated on the same 4DCT for standard ITV-based SABR treatment as well as the Calypso guided SABR treatment. The comparison of the PTV volumes will be calculated as follows:

$$\% \text{ change in PTV} = (\text{PTV}_{\text{standard SABR}} - \text{PTV}_{\text{Calypso Guided SABR}}) / (\text{PTV}_{\text{standard SABR}}) \times 100$$

This metric will be reported as a mean for the cohort with SD

Quality of Life Data: The mean EORTC QLQ – LC13 plus standard deviation will be tabulated in descriptive format for each evaluation time point.

Acute and Late Toxicity: The maximum grade of observed toxicity during treatment and follow-up will be tabulated in a descriptive format by adverse effect.

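### The Phase II 40% hypothesis and the stated power of 0.92 are written for different quantities from the primary endpoint

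*Combined protocol and SAP*

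**What the plan says.** Three places describe the Phase II comparison of planning target volumes.

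- **Section 6.0, Study Hypotheses.** "The Median Planning Target Volume (PTV) of Calypso guided respiratory gated SABR will be 40% smaller than the median PTV volume". The comparator is the conventional ITV technique, so this compares two cohort medians.
- **Section 7.0, Primary Endpoints.** "Mean within patient difference in PTV volumes of standard ITV-based SABR compared to gated SABR utilizing Calypso based PTV margins". The result is to be given in percentage terms. Section 13.0 (Endpoints) gives the formula for each patient, takes both volumes from the same 4DCT, and says: "This metric will be reported as a mean for the cohort with SD".
- **Section 13.0, Study Power.** The sample size is justified as enough "to detect a 40% reduction in the mean PTV volume between standard ITV based SABR treatment as compared to gated calypso guided SABR". The significance level is 0.05, one-sided. The inputs are a published median PTV of 62.9 cm³, an SD of 43.6 cm³ and 28 patients. Section 1.0 assigns 26 of the 28 to Phase II.

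No section reconciles the three. None names a test, a null value or a confidence interval for the endpoint.

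**The concern.** The endpoint, the hypothesis and the power calculation should refer to one quantity. Here they refer to three: a mean of paired percentages, a ratio of two unpaired medians, and a change in mean volume, in which large targets carry most weight.

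Two things are at stake. First, if the result falls near 40%, the report could say that the hypothesis was or was not borne out according to the section followed, and that choice could be made after the data are seen. Second, the only power figure in the plan was not calculated for the endpoint it appears to support. The hypothesis sentence also ignores the pairing within patients on which the comparison is built.

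**Working it through.** **1. Reproduce the stated power.** Inputs from Section 13.0: location 62.9 cm³, SD 43.6 cm³, n = 28, one-sided alpha 0.05.

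- Difference: 0.40 × 62.9 = 25.16 cm³.
- Standard error: 43.6 / √28 = 8.24.
- Power: Φ(25.16 / 8.24 − 1.645) = Φ(1.409) = 0.9205, which matches 0.92.

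Other forms fit less well: one-sample t, one-sided, 0.908; one-sample z, two-sided, 0.863; two-sample, one-sided, 0.697 with 28 per group or 0.453 with 14 per group. So 0.92 belongs to a one-sample, one-sided test of a shift in mean volume in cm³ against no difference. A published median stands in for the mean. The between-patient SD of a single PTV stands where a paired analysis needs the SD of the within-patient difference.

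With the Phase II number, the same formula gives Φ(25.16 / (43.6 / √26) − 1.645) = Φ(1.298) = 0.903.

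**2. Show that the three quantities differ.** Let s and c be a patient's standard and Calypso volumes.

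- Hypothesis: 1 − median(c) / median(s)
- Endpoint: mean of (s − c) / s
- Power statement: 1 − mean(c) / mean(s)

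They coincide only in special cases, such as the same percentage reduction in every patient. The five patients below are constructed, with s = 20, 40, 62.9, 90 and 150 cm³ (sum 362.9).

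| Reductions by patient (%) | Sum of c (cm³) | Hypothesis | Endpoint | Power statement |
|---|---|---|---|---|
| 50, 45, 40, 35, 30 | 233.2 | 40.0% | 40.0% | 35.7% |
| 30, 35, 40, 45, 50 | 202.2 | 40.0% | 40.0% | 44.3% |
| 48, 46, 38, 36, 34 | 227.6 | 38.0% | 40.4% | 37.3% |

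Third row: the endpoint is 202 / 5 = 40.4; the median comparison is 1 − 39.0 / 62.9 = 38.0%; the mean-volume comparison is 1 − 227.6 / 362.9 = 37.3%. The endpoint passes 40% and the other two fall short.

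**3. Ask how often they split around 40%.** This needs inputs that the documents do not give. Assume 26 patients, lognormal standard PTVs with the plan's median 62.9 and SD 43.6, a true mean within-patient reduction of 40% with an SD of 8 to 15 points, and a correlation with log volume between −0.5 and 0.5.

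- The three estimates were not all on the same side of 40% in about 43% to 59% of simulated trials.
- The expected reduction in mean volume ran from 36% to 44% while the endpoint's expectation stayed at 40%.
- The median comparison varied about twice as much from trial to trial as the endpoint (SD 3.5 to 5.7 points against 1.6 to 2.9).

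Away from 40% the conflict fades. One geometric model assumed capsule-shaped targets 1 to 3.9 cm across, median motion about 1 cm and a quarter of the motion left in the gating window. With true reductions of about 44% to 48%, the three split in about 5% of trials; above 50%, in essentially none. Other assumed geometries gave anything from near 0% to about 70%. These models produced standard PTVs well below the plan's 62.9 cm³ (a median near 32 cm³ in the one described), so they do not settle the frequency.

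**4. Consider power for the endpoint itself.** In percentage terms the plan's inputs imply an SD of 43.6 / 62.9 = 69 points. The documents give no SD for the within-patient percentage change. If it were 30 points (assumed), 40 / (30 / √26) = 6.80 and power against zero is Φ(6.80 − 1.645), above 0.99. At 10 points it is higher still.

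**The case against.** The strongest reply is that the governing quantity can be identified. Section 7.0 names it under Primary Endpoints and Section 13.0 repeats it with a formula. Only one hypothesis sentence and the power wording depart from it. This stands: a reader might infer that the plan leaves its primary endpoint undefined, and it does not. The loss of pairing likewise affects the hypothesis sentence, not the endpoint.

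It also stands that no section requires the estimate to reach 40%. A reader might infer that the trial could be declared both positive and negative from one dataset. The documents do not support that. In Section 6.0 the 40% is a prediction, and in Section 13.0 it is the effect to be detected, apparently against no difference. Against a null of zero, all three quantities would ordinarily agree. If the point estimate did have to reach 40%, the chance would be only about one half when the truth is exactly 40%.

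A third tempting inference is that the endpoint must exceed the reduction in mean volume, because a fixed margin cut removes a larger share of a small target. Section 2.0 says larger tumours gain more from gating, which pulls the other way, and the second row of the table shows the order reversed. The direction is not settled by the documents.

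Finally, 0.92 is not an arithmetic error, and nothing here shows that too few patients are planned for a test against no reduction.

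What survives is that the hypothesis and the power figure do not belong to the stated endpoint, and that no named test or interval supplies another basis for the conclusion.

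**Conclusion.** The point holds as a mismatch around an identifiable primary endpoint. The hypothesis compares medians, and the power is for a mean volume in cm³ with a single-volume SD and n = 28. The endpoint is a mean paired percentage in 26 Phase II patients. In the constructed examples the three quantities differ by up to about 4 percentage points and can straddle 40%. The effect is confined to how a result near 40% is described against the Section 6.0 hypothesis. Its frequency cannot be fixed from the documents: 43% to 59% when the truth is 40% under the lognormal assumptions above, and close to nil when the true reduction is well above 40%. On the plan's own formula, power is 0.90 rather than 0.92 at n = 26. Power for the actual endpoint is unknown until an SD is assumed, and is probably higher.

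**What to change.** - Keep the endpoint of Sections 7.0 and 13.0 as the single primary contrast. Reword the Section 6.0 hypothesis as a mean within-patient percentage reduction in PTV, with 40% as its expected value.
- In Section 13.0, name a paired one-sample test of that mean against a stated null (no reduction, as the power calculation implies) and a confidence interval. Show 40% as the expected value against the interval, not as a pass mark.
- Recompute the power for this endpoint with n = 26 and an assumed SD of the within-patient percentage change shown over a range, for example from 10 points up to the 69 implied by the present inputs. Otherwise withdraw the 0.92. Changing the words alone would leave that figure attached to an endpoint for which it was not calculated.
- Report the median PTV per technique and the reduction in mean volume as descriptive only.

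The cost is edits to Sections 6.0 and 13.0 and one short recalculation, with no new patients or data. The stated power must be presented as conditional on an assumption, and the freedom to choose among summaries is lost.
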